6.13.4 Time to Hemostasis from Patient Randomization (TTHR)

Time to Hemostasis from patient randomization (TTHR) (minutes) will be collected and displayed with descriptive statistics. TTHR is defined as time from randomization until hemostasis (in case of event) or 10 minutes observation end in case of censoring. Kaplan-Meier curve will be used to estimate the median TTHR in each treatment group. KM parameters and analyses will be tabulated in an analogue manner like in sec. 6.13.3.

6.13.5 Percentage of all Patients who achieved Hemostasis at 10 Minutes after first Product Application

Number and percentage of all patients (patients that achieved hemostasis with a single patch application and patients that required additional patches) that have achieved hemostasis 10 minutes after first product application and therefore did not need to convert to standard of care treatment at the end of these 10 minutes will be tabulated.

Data will be presented with descriptive statistics and 95% confidence intervals of the difference between treatments.

A stratified analyses by one-patch applicants and more than one patch users may be done depending on the results of the BDRM using strata single patch users and additional patch users. In case it is decided to perform a stratified analysis a table will be added to show number/ percentages of patients with one patch and with >1 patches.

6.13.6 Incidence of Treatment Failure

Incidence of treatment failure is defined on treatment failure criteria according to section 11.1.3 of the protocol:

- in case the bleeding at TBS (or re-bleeding) is still observed after 10 minutes following first application of study product;
- if hemostasis at TBS is achieved, but the Investigator decides that an additional treatment is required to ensure the durability of hemostasis;
- if there is a breakthrough bleeding requiring treatment other than the study product, at any time

Data will be presented only with the appropriate descriptive statistics and exact Clopper Pearson 95% confidence interval of the difference between treatments

	STATISTICAL ANALYSIS PLAN	FSTAT.01.03
Study Code: HEM-HEM-01-17		Sealantium Medical Ltd.

6.13.7 Incidence of Transfusion Requirements

The number of patients requiring transfusion during the 6 months follow up period will be determined.

Data will be presented only with the appropriate descriptive statistics and exact 95% Clopper-Pearson confidence interval of the difference between treatments.

6.14 Previous and Concomitant Medication

Tables will distinguish between previous and concomitant medication with respect to start of medication compared to time point of surgery/ patch insertion. All medication starting before reference time point (first product application) are previous, all starting at or after reference time point will be concomitant.

All medications reported in the CRF, categorized by medication group according to WHO DRUG Dictionary DDE enhanced [version 2022 DDE+HD], ATC1 and ATC4 level will be summarized displaying number of medications in the specific ATC1 and ATC4 class, as well as number and percentage of patients taking it within each ATC1 and ATC4 class.

The number and percentage of patients using at least one medication within each medication group will be presented by time point (previous/ concomitant) and treatment.

7 Extent of Exposure

A frequency table showing counts and percentages of patients having applied one patch, two patches, three patches etc. will be shown.

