8.3. Exclusion Criteria

1. Patients having undergone a therapeutic surgical procedure within 30 days from the study enrolment.
2. Patients with a severe coagulopathy defined as INR $>$ 2.0.
3. Patients with platelet count $<$ 50,000 $\times 10^9$ PLT/L at the screening (ref. 11).
4. Patients admitted to trauma surgery.
5. Transplant patients due to fulminant hepatic failure.
6. Patients with known or suspected allergy or hypersensitivity to blood products or to one of the components of sFilm-FS or the active-comparator.
7. Patients with anesthesia risk judged to be higher than ASA3 by the Investigator.
8. Patients with at least one of the following concomitant conditions: severe co-morbid conditions known to pose a high risk for surgery and adequate recovery (i.e., liver cirrhosis Child-Pugh with score B or C, cholestasis, heart diseases), immunodeficiency diseases, blood clotting disorders, any conditions known to effect wound healing (i.e., collagen vascular disease), known or current alcohol or drug abusers.
9. Patients suffering from claustrophobia.
10. Patients with implanted or embedded metal objects, prostheses, pacemaker, or fragments in the head or body that would present a risk during the MRI scanning procedure or have worked with ferrous metals either as a vocation or hobby or following trauma (i.e., sheet metal workers, welders, or machinists) in such a way that might have led to unknown, indwelling metal fragments that could cause injury if they moved in response to placement in the magnetic field.
11. Patients being treated with at least one of the following treatments: antibiotic therapy for active infection, fibrin sealants, systemic steroids, or immunosuppressive agents.
12. Patients who are participating or have participated in other clinical studies within the 30 days before the study enrolment.
13. Female patients who are pregnant or breast-feeding or who wish to become pregnant during

the period of the clinical study and for three months later.

14. Female patients of childbearing age (less than 24 months after the last menstrual cycle) who do not use adequate contraception.*

Intra-operative exclusion criteria:

15. Patients with a TBS identified with major arterial bleeding requiring suture or mechanical ligation.
16. Patients identified by the Investigator to have intra-operative bleeding from large defects in large arteries or veins, requiring repair.

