10.7. Concomitant Medications

The use of any other topical hemostat, except fibrin sealants or topical thrombin, at the TBS will be permitted once the observational period is completed and hemostasis was not achieved or in the event of breakthrough bleeding requiring further treatment (as deemed necessary by the Investigator).

For additional bleeding sites, separate from the TBS, patients must be treated with the same study article according to the randomization assignment, when clinically appropriate. If other hemostatic products are needed the Investigator should revert to his/her standard of care (excluding fibrin sealants and topical thrombin).

Administration of all medications, including indication, dose, frequency, and route of administration will be recorded in the source documentation file and in the electronic Case Report Form (eCRF). All concomitant medications will be discussed and documented at each visit.

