14.7.3 Concomitant Therapies

Descriptive statistics such as frequency counts and percentages of Patients who use concomitant therapies will be provided by ATC therapy category, preferred term and also by treatment group.

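### SAP 6.14 sorts medication by start time alone, so drugs carried across product application count only as previous and the concomitant counts are too low

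*SAP*

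**What the plan says.** SAP section 6.14 gives the basis of the split: "Tables will distinguish between previous and concomitant medication with respect to start of medication compared to time point of surgery/ patch insertion". The next sentence fixes the cut-off: "All medication starting before reference time point (first product application) are previous, all starting at or after reference time point will be concomitant". Patient counts per medication group "will be presented by time point (previous/ concomitant) and treatment". There are two categories, and none for a drug started earlier and still being taken.

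Protocol section 14.7.3 plans that "Descriptive statistics such as frequency counts and percentages of Patients who use concomitant therapies will be provided by ATC therapy category", by treatment group. It does not restrict this to drugs newly started after application. Protocol section 10.7 adds that "All concomitant medications will be discussed and documented at each visit". The Schedule of Assessments collects concomitant medications from screening onward, and section 11.1.2 records them for the 24 hours before surgery. The protocol thus applies the word to treatment already under way before the patch.

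Three other SAP sections bear on this. Section 6.10 keeps concomitant medications out of the baseline tables. Section 6.1 has all CRF data listed by treatment group, subject and visit. Section 9.1, on changes to the analyses, deals only with the analysis populations.

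**The concern.** A concomitant-medication table is normally read as the answer to one question: what else were patients taking while outcomes were being observed? A rule based on start time answers a different one: what was newly started after the patch?

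The difference matters for interpreting safety, which is the primary endpoint. Protocol section 12.1 follows bleeding at the target site, thrombotic events and transfusion-related complications from randomization to the last visit, about six months after surgery. A reader of those events would want to see, by arm, ongoing treatment that affects bleeding or clotting.

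Such treatment is not ruled out at entry. The treatments excluded in protocol section 8.3 are "antibiotic therapy for active infection, fibrin sealants, systemic steroids, or immunosuppressive agents"; anticoagulants and antiplatelets are not among them. The numerical coagulation limit excludes "Patients with a severe coagulopathy defined as INR" above 2.0. Clotting disorders are excluded as a condition, but that criterion names no drug class. In small arms (15 completers each are planned), a chance imbalance in such drugs is possible, and the concomitant table is where a reader would look for it.

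**Working it through.** The plan states no figure on this point, so there is none to reproduce. The check applies the rule to cases and then sets out what the two tables can and cannot show.

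**Step 1. Rules compared.** Time 0 is first product application.
- SAP rule: start < 0 is previous; start ≥ 0 is concomitant.
- Overlap rule: stop < 0 is previous; any use at or after 0 is concomitant.

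**Step 2. Five hypothetical patterns** (chosen for illustration, not taken from the documents).

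| Pattern | SAP rule | Overlap rule |
|---|---|---|
| Day -20 to Day -5 | previous | previous |
| Day -20, ongoing to Day 180 | previous | concomitant |
| Started in theatre 1 hour before the patch, to Day 10 | previous | concomitant |
| Started at application | concomitant | concomitant |
| Started Day 1 | concomitant | concomitant |

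Two of the five change, and both are drugs carried across the moment of application. The third row arises because the cut-off is the patch and not the start of surgery. The first and second rows get the same SAP label although one drug ended before surgery and the other ran through all of follow-up.

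**Step 3. Size of the shortfall.** Take one ATC class in one arm. Let
- N = patients with at least one start at or after application (the SAP concomitant count);
- P = patients with at least one start before application (the SAP previous count);
- K = patients whose only use after application is a drug started before it.

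The overlap concomitant count is N + K. The shortfall is (N + K) − N = K. Every one of these K patients is also in P, so 0 ≤ K ≤ P. The SAP tables give N and P but not K, because P mixes drugs that stopped with drugs that continued. Nothing in the protocol or SAP gives the frequency of long-term medication, so K cannot be narrowed further.

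**Step 4. Is it repaired elsewhere?** The baseline section does not report these drugs (SAP 6.10). The change log does not mention the narrower meaning (SAP 9.1). The listings hold the entries (SAP 6.1) but give no summary by arm. The table shells are in a separate document (SAP 11.2) and could not be checked.

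**The case against.** The strongest reply is that this is a matter of labelling. SAP 6.14 summarises every medication in the CRF at ATC1 and ATC4 level, so a continuing anticoagulant does appear, by arm and class, under *previous*. The listings carry it too. That stands: a reader might infer that long-term drugs vanish from the report, and they do not.

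A second reply is that the protocol never defines the term. Section 14.7.3 could mean all recorded medication, which the two SAP categories cover between them. This weakens any claim that the SAP breaks an explicit definition. It does not rescue the output. On that broad reading the table headed *concomitant* is only part of what was promised; on the usual reading, use during the observation period, its counts are too low.

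Two further inferences are tempting and go too far:
- **That a long-term class would show zero concomitant users.** Patients who newly start a drug of the same class at or after application are counted. A drug paused for surgery and resumed might also count, if the restart is entered as a new record; the documents do not say. Only the patients in K contribute nothing.
- **That the safety or efficacy results are distorted.** The label feeds no endpoint, analysis set, adjustment or confidence interval. Adverse events are tabulated independently of it, and SAP 6.6 calls all results exploratory.

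It is also fair to object that the stop date is an assumption. Protocol 10.7 lists indication, dose, frequency and route among the recorded items, not stop date or ongoing status, and the eCRF is not available here.

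**Conclusion.** The point holds as a reporting defect of limited weight. As written, the rule places every drug carried across first application, including one begun earlier in the same operation, in the previous table only. The concomitant count in each class is short by K, the continuing users with no new start in that class. K lies between 0 and the previous count for the class, and the planned tables do not allow it to be found. Neither table shows medication use during the six-month safety period.

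The classification itself follows from the wording of SAP 6.14 and needs no numerical assumption. Calling the counts too low takes concomitant to mean used during the observation period. The practical size depends on how many patients continue long-term drugs, which the documents do not give. The conclusion also assumes that the separate table shells add no marker for ongoing drugs.

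**What to change.** Replace the classifying sentence in SAP 6.14. Previous: stopped before first product application. Concomitant: taken at or after first product application, whatever the start date. If the sponsor wants to keep newly started drugs visible, use three categories instead: stopped before application, started before and ongoing, and started at or after application. The second and third together, counting each patient once, then give the protocol 14.7.3 count.

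State the data source. Use the stop date or an ongoing flag if the eCRF records one. Otherwise derive continued use from the medication records made at each visit, and say how a drug with an unknown stop date is classed.

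The cost is one sentence, a matching change to the table shells and a small programming change. If no stop date or ongoing flag was collected, working from the visit records adds some data handling. SAP section 2 has the plan finalised after the blind data review meeting and before database lock, so the change fits within that step.

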8 INTERIM STATISTICAL ANALYSIS

Not applicable.

9 Changes to the Analyses/ Endpoints

9.1 Changes to the Analyses

The definition of the analyses populations in the protocol was extended:

The ITT population was renamed to Full-analysis Set (FAS) to be in concordance to the ICH GCP E9 Statistical Guideline [2].

In the same Guideline it is explained that a Per-Protocol Set (PPS) is the one without major violations. A PPS was added.

As the efficacy results are fully explorative, all three analyses sets FAS1, FAS2 and PPS will be used without further distinguishing on which main conclusions will be drawn.

	STATISTICAL ANALYSIS PLAN	FSTAT.01.03
Study Code: HEM-HEM-01-17		Sealantium Medical Ltd.

9.2 Changes to the Endpoints

Originally the endpoint TTHR was not planned to be analyzed according to protocol. However the sponsor still wants to see data about it and the analysis of this endpoint was added.

	STATISTICAL ANALYSIS PLAN	FSTAT.01.03
Study Code: HEM-HEM-01-17	Sealantium Medical Ltd.	

11.1 Appendix 1: Mock listings

see separate document

11.2 Appendix 2: Mock tables

see separate document
